## Section D. Abbreviations

Define all unusual or 'technical' terms related to the research. Add or delete rows as appropriate. Maintain alphabetical order for ease of reference.

BMI	Body Mass Index
BOLD	Blood-Oxygen Level Dependent
BRC	Biomedical Research Centre
CNS	Central Nervous System
CUREC	Central University Research Ethics Committee
DHEA	Dehydroepiandrosterone
DSM-V	The Diagnostic and Statistical Manual of Mental Disorders, Fifth Edition
ECG	Electrocardiogram
EGNG	Emotional Go/No-Go Task
EMA	European Medicines Agency
FDA	Food and Drug Administration
FERT	Facial Emotional Recognition Task
fMRI	Functional Magnetic Resonance Imaging
FMRIB	Oxford Centre for Functional MRI of the Brain
GAD-7	Generalised Anxiety Disorder Assessment
GCP	Good Clinical Practice
GP	General Practitioner
H 3 R	Histamine-3 receptor
ICF	Informed Consent Form
ICF	Informed Consent Form

MHRA	Medicines and Healthcare products Regulatory Agency
MRI	Magnetic Resonance Imaging
MS IDREC	Medical Sciences Interdivisional Research Ethics Committee
NICE	National Institute for Health and Care Excellence
OHBA	Oxford Centre for Human Brain Activity
PANAS	Positive and Negative Affect Schedule
PDQ	Perceived Deficits Questionnaire
PEACE	Pitolisant effects on affect and cognition exploratory (study)
PFC	Prefrontal Cortex
PHQ-9	Patient Health Questionnaire
PI	Principal Investigator
PILT	Probabilistic Instrumental Learning Task
PIS	Participant Information Sheet
PPI	Personal Protective Equipment
SCID	Structured Clinical Interview for DSM-5
SCID	Structured Clinical Interview for DSM-5
SOP	Standard Operating Procedure
VAS	Visual Analogue Scale
WIN	Wellcome Centre for Integrative Neuroimaging

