## **2. Subsequent Visits**

### Study Visit

Participants who are medically approved to take part in the study after the screening visit are invited to take part in the study visit. Prior to the study visit, and after the screening visit, participants will be randomised using the variance minimisation algorithm described above to ensure a balance of covariates of interest across treatment and placebo groups. The randomisation code will be drawn up by a researcher not involved in the study using an randomisation procedure known as variance minimisation, following a procedure outlined by Sella, Raz & Cohen Kadosh (2021). Participants will be allocated to placebo or treatment groups based on gender, level of education, and their digit span score (as an index of general intelligence). Allocation of treatments will be recorded on a Randomisation List which will be updated when each new participant enters the randomised phase. The Randomisation List will be held securely within the Neurosciences Building by the study medic ([name]). Pitolisant and placebo agents will be kept securely within a locked medicines cabinet also within the Neurosciences building.

During the visit, participants will receive either a single dose of pitolisant (36mg single dose) or placebo. They will receive the dose at the Neurosciences Building, Warneford Hospital site. The study has a double-blind design thus neither the researchers nor the participant will know whether pitolisant or placebo is given. On arrival, participants will briefly be reviewed to ensure the inclusion criteria are still satisfied. Prior to drug or placebo administration, the following procedures will be undertaken:

- Inclusion/exclusion criteria review

- Completion of the MRI screening form (APPENDIX H - 3T VOLUNTEER SCREENING FORM) once more to ensure it is still safe for them to undergo fMRI scanning.
- Clinical screening, mood and side effects questionnaires (to establish baseline) on qualtrics – PHQ-9, GAD-7, PANAS, PDQ and Need for Cognition Scale

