Providing eligibility still holds following review, participants will then take the single dose of pitolisant or placebo. There will then be a two-hour monitoring period to allow for the drug (where appropriate) to metabolise and activate within the system. Participants will then be escorted to OHBA where they will undertake an MRI scan (or, fMRIB if nil capacity at OHBA). First participants will be asked to change into MRI safe scrubs and screened for MRI safety by the scan operator / radiographer. MRI scans will be undertaken in accordance to the CUREC approved MRI scanning procedure (APPENDIX M - CUREC APPROVED MRI INVESTIGATIONS PROCEDURE). The scan itself will include:

- Structural scan (T1 and T2-weighted imaging)
- Probabilistic Learning Task (fMRI) – this task requires participants to choose one of two pairs of symbol every trial. One of these pairs will be associated with a win probability and the other not, with each pair corresponding to reciprocal probabilities. Participants are asked to make choices based on what symbol will maximise their win-loss ratio and increase monetary outcome. Participants will be instructed that they will be reimbursed at the end of the study based on their performance during this task (participants can win up to £20 total depending on performance).
- Memory task (fMRI) – This task requires participants to learn presented emotionally neutral stimuli (images) prior to the scan, then during the scan they will be asked to recall if the stimuli presented during the scan were previously seen using a two-button press.
- Verbal *n*-back task (fMRI) – it will require participants to concentrate on a series of letters (upper case and lower case) stimuli displayed centre-screen and pressing a button according to a rule provided before each block (e.g. press spacebar if you see an image you previously saw three images ago).
- Resting State fMRI – this will not require participants to perform any tasks and will take approximately 7 minutes to complete
- Arterial spin labelling
- Physiological recordings including pulse, respiration, and skin conductance – recorded using a pulse meter, respiration bellows and electrodes strapped by Velcro to fingertips.
- Eye tracking

Once the scanning has completed (approximately 1.5 hours), participants will be escorted back to the Neurosciences Building, Warneford Hospital site. Here, participants will complete the remaining:

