**3. Have you done a sample size calculation?**

Yes  No

If yes, please give details below

If no, please give details to indicate you have considered the implications the selected sample size will have on the research outcome

The selected sample size was informed by a priori statistical power analysis (APPENDIX P – POWER CALCULATION READ-OUT) for a one-way fixed effects ANOVA approach within a healthy volunteer population via G\*Power Software (Statistical power: 80%; Estimated effect size: 0.4; Alpha level: 0.05), which requires a total sample size of 52 to power (an additional 4 persons will be recruited in case of data quality issues and/or drop-out). The sample size calculation is conservative and informed by a previous placebo-controlled cross-over study of cognitive function in healthy volunteers (N=16) following a short course of an histamine-1 agonist/histamine-3 antagonist (betahistine). The study demonstrated large between-group differences in n-back accuracy ( $\eta_p^2 = 0.74$ ) and BOLD activation within the Inferior frontal gyrus and medial temporal gyrus during the n-back task ( $\eta_p^2 = 0.78$  and  $\eta_p^2 = 0.79$ , respectively).

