#### 4. Analysis of Outcome Measures

R Software will be used to analyse all psychometric, cognitive and neuroimaging data. Sample characteristic data (e.g. age, gender, and years in education) will be analysed using an appropriate analysis of variance (e.g. t-test or Mann-Whitney U), depending on model assumptions being satisfied. Cognitive and neuroimaging data will be analysed using a between-groups ANOVA approach, with appropriate normality transformations and Greenhouse–Geisser correct where the distribution and/or degrees of freedom does not meet model assumptions. Post-hoc analyses will be corrected using Bonferroni (or Bonferroni-Holm) correction. Analysis of fMRI endpoints will be completed using the FSL software package.

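### Capacity decides which of two centres scans a participant, and neither the allocation nor the stated imaging model accounts for scanner, so the imaging comparisons can lose precision

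*Protocol*

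**What the plan says.** **Scanner.** In Section G.2 (Study Visit), after dosing and a two-hour wait, participants are "escorted to OHBA where they will undertake an MRI scan (or, fMRIB if nil capacity at OHBA". The abbreviations list in Section D expands FMRIB as "Oxford Centre for Functional MRI of the Brain" and lists OHBA separately, so these are two centres. The protocol text sets no limit on the number of FMRIB scans and does not say that the scanners are matched or that the data will be harmonised.

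**Allocation.** The same section says: "Participants will be allocated to placebo or treatment groups based on gender, level of education, and their digit span score". On timing it says: "Prior to the study visit, and after the screening visit, participants will be randomised using the variance minimisation algorithm". Scanner is not among the factors.

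**Analysis.** Section J.4 says: "Cognitive and neuroimaging data will be analysed using a between-groups ANOVA approach". It adds: "Analysis of fMRI endpoints will be completed using the FSL software package". It names no scanner term.

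**Sample size.** Section J.3 sizes the trial for a "one-way fixed effects ANOVA approach within a healthy volunteer population via G\*Power Software", with these inputs: "Statistical power: 80%; Estimated effect size: 0.4; Alpha level: 0.05), which requires a total sample size of 52 to power". Four more participants bring the total to 56, or 28 per group. There is no allowance for variance between scanners.

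**The concern.** The imaging outcomes are differences between two groups of people who are each scanned once. In a cross-over trial with both scans on one machine, a scanner offset would cancel within the person. Here it cannot. If the two centres give systematically different BOLD, resting-state or perfusion values, the offset acts in two ways:

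- the arms may by chance send different numbers to FMRIB, which shifts the observed contrast in that one trial;
- even with equal numbers, the offset adds to the residual variance if the model ignores it.

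These are two views of one cost. Averaged over chance splits, the shift is part of the extra variance, so the two must not be added together.

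The trial minimises in order to balance covariates, yet its own scanning rule brings in a nuisance factor that neither the allocation nor the stated model handles. Only the imaging outcomes and the tasks done in the scanner are exposed. The tasks done afterwards in the Neurosciences Building are not.

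**Working it through.** **Inputs from the protocol.** Two groups of 28 (N = 56), effect size f = 0.4 (d = 2f = 0.8 for two equal groups), alpha 0.05, target power 80%, stated requirement 52.

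**Assumptions, because the protocol gives no figure.** The number scanned at FMRIB is k = 6, 11 or 17 of 56 (share q = k/56 = 0.107, 0.196 or 0.304). The offset between scanners is D = 0.5 or 1.0 within-scanner SD. Scanner is independent of arm.

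**1. The plan's own figure.** Power comes from the noncentral F distribution with 1 and N − 2 degrees of freedom and noncentrality λ = N f².
- N = 50: 79.1%.
- N = 52: λ = 52 × 0.16 = 8.32, power 80.7%.
- N = 56: λ = 56 × 0.16 = 8.96, power 83.6%.

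The smallest even N that reaches 80% is 52, so the stated figure reproduces. The reference with no scanner effect at the full sample is 83.6%.

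**2. Scanner ignored in the model.** The residual variance is multiplied by V = 1 + D² q(1 − q), and λ becomes 8.96/V with 54 degrees of freedom.

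| FMRIB scans | q(1 − q) | V, D = 0.5 | Power | V, D = 1.0 | Power |
|---|---|---|---|---|---|
| 6 | 0.0957 | 1.024 | 82.8% | 1.096 | 80.2% |
| 11 | 0.1578 | 1.039 | 82.2% | 1.158 | 78.0% |
| 17 | 0.2114 | 1.053 | 81.7% | 1.211 | 76.1% |

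At D = 1.0, 28/V gives the equivalent of 25.6, 24.2 and 23.1 per arm. With only 2 scans at FMRIB, q(1 − q) = 0.0344, and power is 83.3% (D = 0.5) or 82.4% (D = 1.0).

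**3. Scanner in the model.** One degree of freedom is lost (53 remain). The expected chance correlation between arm and scanner reduces λ by the factor 1 − 1/55, so λ = 8.96 × 54/55 = 8.80. Power is 82.9% whatever the offset.

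**4. Chance imbalance.** With scanner independent of arm, the FMRIB count in one arm is hypergeometric (56, 28, k). The probability that the two arms' counts differ by 5 or more is 2.3%, 17.7% and 24.5% for k = 6, 11 and 17. With 4 or fewer FMRIB scans, it is zero. A split of 8 against 3 shifts the contrast by (5/28) × D = 0.09 to 0.18 SD. For scale, the standard error of the contrast is √(2/28) = 0.27 SD and the design effect is 0.8 SD.

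**5. Type I error.** I simulated 200,000 trials for each k with no drug effect, a 1.0 SD offset and an unadjusted two-group test. The test rejected in 5.0%, 5.0% and 4.9% of trials for k = 6, 11 and 17. The unadjusted standard error already covers the chance imbalance.

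**The case against.** **The covariate belongs in the SAP.** A scanner regressor is a usual item of an SAP or imaging plan. Section J.4 excludes no nuisance covariate, and the SAP is not at hand. This stands in part: the omission of the term is the weaker half of the point. But the protocol itself lists the allocation factors and names the model, and a later SAP cannot balance scanner after participants have been allocated.

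**Scanner differences read as a drug effect.** A reader might infer that they would produce spurious drug effects. The documents do not support that. Allocation precedes the visit, the trial is double-blind and the switch depends on capacity, so nothing ties scanner to arm. The simulation shows no excess of false positives.

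**The size is assumed.** This stands. FMRIB is only the fallback, so its share could be close to zero, and at 0.5 SD the loss is at most about two points of power. One MRI procedure (Appendix M) and one 3T screening form (Appendix H) are cited for all scans. Those appendices are not at hand. They may bear on comparability, but what is shown does not establish that the scanners are matched.

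**Dose-to-scan timing.** A reader might also infer that a scan at the second centre changes the interval from dosing to scanning. The protocol gives no distance or travel time to either centre, and participants are escorted to OHBA as well. This cannot be maintained.

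**One scanner for all.** Rebooking visits until OHBA is free would remove the issue. It could also exceed the screening-to-study window (six weeks in Section F.5, four in Section G.1) and trigger rescreening. That is a trade-off for the investigator, not a requirement.

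**Conclusion.** The point holds as a matter of precision. The scanning rule allows two centres, and neither the stated allocation factors nor the stated imaging model accounts for which one was used. Systematic bias and inflated type I error do not follow.

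Under the assumed ranges, ignoring scanner costs between 0.8 and 7.5 points of power at N = 56 (83.6% to 82.8% or 76.1%). Adjustment holds power at about 82.9%. Power drops below the 80% target only in the less favourable cases: 11 or 17 FMRIB scans with an offset of 1.0 SD. With few FMRIB scans, adjusting and not adjusting are practically equivalent. The conclusion rests on the assumed share and offset, on scanner being independent of arm, and on a single comparison at the design effect size.

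**What to change.** - **Section G.2:** record the scanner used for every participant.
- **Section J.4:** state that scanner enters every imaging group model as a prespecified nuisance covariate, and add a sensitivity analysis restricted to OHBA scans.
- **Optional, Section G.2:** where the scanner is already fixed at booking and known before allocation, add it as a minimisation factor. This cannot work if the switch is made on the day.

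The cost is a few lines of protocol text and one degree of freedom per model. With no scanner effect at all, the term would lower power from 83.6% to about 82.9%. The OHBA-only analysis uses fewer participants and should be read as a check on consistency, not as a powered test.

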### 3. Biological Sample Handling

**Urine samples** will be used for drug screening and pregnancy tests. These will be administered at the Screening Visit/Study visit. The urine tests will be administered by a trained staff member using dipstick tests. After the results are obtained the sample will be disposed of. All urine testing will adhere to approved procedure AP24 'taking urine samples'.

### 4. Will the research include any audio, video or photographic recordings?

No.

### 5. Discontinuation/Withdrawal of Participants

Each participant has the right to withdraw from the research at any time. In addition, the Investigator may discontinue a participant from the research at any time if the Investigator considers it necessary for any reason including:

- Pregnancy
- Ineligibility (either arising during the research or retrospectively having been overlooked at screening)

- Significant protocol deviation
- Significant non-compliance with treatment regimen or research requirements
- Withdrawal of consent
- Loss to follow up

If a participant is withdrawn, no further procedures or observations will continue to be required. Withdrawal from the study will result in exclusion of the data for that participant from analysis. Withdrawn participants will be replaced. The reason for withdrawal if given will be recorded in the Participant Log of the Research Master File.

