	
(5%). Most relevant to this protocol is its tolerability profile in a single dose (40mg) in healthy volunteers, where 1 in 6 participants experienced increased sleep duration, dystonia and dizziness. A recent study in healthy volunteers showed no cardiac safety signals in individuals taking up to the maximum dose of pitolisant (36mg/day).
 
In this study, we will use a single dose of 36mg pitolisant within its recommended dose range (4.5–36 mg/day). Study participants will be screened to exclude those presenting with QT prolongation via ECG assessment as cautioned by the FDA, in addition to cautions contraindications for those with gastrointestinal disorders, epilepsy, mental health difficulties, clinical eating disorders and severe obesity by NICE.

--	---

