- Affect, Mood, Subjective Cognition and Side Effects questionnaires (for end-point):
  - PHQ-9
  - GAD-7
  - Visual Analogue Scale
  - Perceived Deficits Questionnaire
  - Side Effects Questionnaire
  - PANAS
  - Need for Cognition Scale
- Instrumental *n*-back task – this widely used task will be done after scanning is complete; it will require participants to complete a version of the *n*-back task in the scanner, but this time participants are rewarded or punished for performance. Participants will start with £1.00 and can earn up to £10 based on performance (similar to the PILT), but cannot lose less than £0.00. This task will involve more complex levels of working memory processing (including 4-back, 5-back).
- A change detection task – a short task of visual working memory which requires participants to view an array of ‘items’ (e.g. coloured blocks) for a short period of time, and after a short period they are shown the same array once again with one subtle change (e.g., one colour has been changed). Participants must identify the change.

- Emotional Go/No-Go task (EGNG) -- this task follows a 'go/no-go' format where participants will be presented stimuli on-screen which they are instructed to either press a button for 'go' trials or inhibit their response. Emotional and non-emotional distractors will be used to check the effect of emotional distraction on response inhibition.
- Facial Emotional Recognition Task (FERT) – the widely-used task will ask participants to recognise the emotion of faces displayed on the screen in sequence; emotions include: sad, surprised, angry, disgusted, happy, neutral).

Once participants had completed these procedures then the study visit will end. Before leaving, participants will be given a wallet-sized card with key details about the study and contact information of a member of the study team to contact if they have any questions. The card will also include the phone number of the out-of-hours BRC on-call medic service in case they need medical advice related to the study out of standard office hours. At the end of this visit, participants will be advised not to drive, cycle or operate machinery, in case they experience any side effects from the drug. To ensure participants get home safely after the visit, the researcher will either arrange a taxi or travel expenses (e.g. bus tickets) for the journey will be reimbursed.

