Participants will be followed-up the day following the study visit with a mood/side effects questionnaire in addition to debriefing and reimbursement details processing. This follow-up should between 30-45 minutes to complete.

The cognitive tasks include measures of executive functioning, decision making and memory. Memory ability is measured through the fMRI memory and instrumental n-back tasks, both of which require participants to recall presented stimuli at a later date. The EGNG will measure response inhibition (executive functioning), requiring participants to continuously press a keyboard input while occasionally being prompted to inhibit their response; this task will rely on affective prompts (e.g. a face with a particular emotional expression) or non-affective prompts (e.g. a phrase such as "do not press spacebar"). The FERT measures emotional processing, and involves the presentation of faces displaying different emotions. In another task of instrumental learning (PILT), participants will be asked to choose between shapes, some of which lead to winning money and some of which lead to losing money – participants will be able to win up to £10 which will be added to the reimbursement they receive at the end of the study. All stimuli will be presented on a computer screen and participants will be required to respond via button presses on a keyboard.

Mood questionnaires are short self-report inventories, including PHQ-9, GAD-7, Need for Cognition Scale, and Positive and Negative Affect Scale.

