## 2. Reporting procedures for serious adverse events or reactions

Any adverse event (AE) occurring to a participant will be reported to the MS IDREC. Reports of related (resulted from administration of any of the research procedures) and unexpected (the type of event is not listed in the protocol as an expected occurrence) adverse events will be reported as soon as possible once the Principal Investigator becomes aware of the event. Unrelated/expected adverse events will be reported within 10 working days of the Principal Investigator becoming aware of the event.

All SUSARs will be reported to the MHRA in addition to the MS IDREC. For fatal and life-threatening SUSARs, this will be reported as soon as possible, but no later than 7 calendar days after the PI is first aware of the reaction. Any additional relevant information will be reported within 8 calendar days of the initial report. Non-fatal or non-life-threatening SUSARs will also be reported as soon as possible, and no later than 15 days after the PI is first aware of the reaction.

All reports to the MHRA will be via the [Yellow Card Scheme](#).

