**2. Provide details about the safety monitoring of participants and the staff/researchers carrying this out**

On the study visit, where the participant will either take a single dose of pitolisant or placebo, participants will be advised to have not consumed alcohol within the past 24 hours. Participants will be asked to arrive via walking or public transport or taxi, and will be asked to continue to avoid driving, operating heavy machinery or using a bicycle for at least the following 12 hours (maximum half-life of pitolisant). All participants will receive a phone number for calling an out-of-hours BRC on-call medic service in case they need medical advice related to the study after the study visit has taken place.

The randomisation code will be broken if a participant requires treatment for a new medical condition/experiences serious adverse reactions and either of these situations make it clinically important to know what medication they are taking. In order to unblind the participant, the study medic/delegated medic will have access to the randomisation code and can unblind if necessary within a maximum of 1 hour. If breaking the code is necessary then only that individual's code will be broken. Data from unblinded participants will not be admitted to analysis. If unblinding occurs, the researcher will record the reason and result of the unblinding, as well as the date and time of the event.

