**3. Give details on the medical cover required and who will provide this cover**

A medical doctor who is part of the research team will review the screening and make a final judgment about including participants in the study. A qualified medical doctor will be contacted if a participant expresses concern to a named researcher regarding side effects or health status changes during the study week.

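### Section G.5 drops the scheduled side-effect questionnaires after withdrawal, with no exception for participants who have already taken the capsule

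*Protocol*

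**What the plan says.** Section G.5 of the protocol lets a participant leave at any time and lets the Investigator discontinue one at any time, for reasons that include pregnancy, ineligibility found late and protocol deviation. It then states: "If a participant is withdrawn, no further procedures or observations will continue to be required". The next sentence excludes a withdrawn participant's data from analysis.

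Section G.2 (Study Visit) describes what follows the capsule. First, "There will then be a two-hour monitoring period"; then a scan of about 1.5 hours; then a set of end-point questionnaires, one of which is a Side Effects Questionnaire. Finally, "Participants will be followed-up the day following the study visit with a mood/side effects questionnaire".

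The safety provisions are in Section I:
- I.2: "Any adverse event (AE) occurring to a participant will be reported to the MS IDREC".
- I.3, item 2: "All participants will receive a phone number for calling an out-of-hours BRC on-call medic service". Participants are also told not to drive, cycle or operate heavy machinery for at least 12 hours, which the protocol gives as the maximum half-life.
- I.3, item 3: "A qualified medical doctor will be contacted if a participant expresses concern to a named researcher regarding side effects".

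**The concern.** The dose is single and taken on site, so everyone who withdraws after swallowing the capsule has had the full exposure that the study intends. Stopping research tasks at that point is reasonable. Ceasing to ask about side effects is a different matter, and G.5 treats the two alike.

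At stake is whether side effects are actively asked about in exposed people. Item 10 of the drug summary table treats single-dose data at 40 mg in healthy volunteers as the most relevant to this protocol, and reports that "1 in 6 participants experienced increased sleep duration, dystonia and dizziness". Of the two scheduled questionnaires, only the next-day one follows a night's sleep. If its content covers sleep, it is the only scheduled question that could pick up a change. Feeling unwell is also a plausible reason to stop, so the people no longer asked may be among the more informative ones.

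**Working it through.** The plan gives no figure on this point, so there is none to reproduce. The check is to set the sections side by side and count what remains required.

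**1. Is there an exception for dosed participants?** G.5 contains none. G.2 (Study Visit) describes the questionnaires only as part of the normal sequence. Section I, on definitions, reporting, monitoring, medical cover and incidental findings, does not restore either questionnaire after withdrawal.

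**2. Scheduled side-effect questionnaires after dosing (G.2).** End of visit: 1. Next day: 1. Total: 2.

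| Point of withdrawal after the capsule | Already completed | No longer required |
|---|---|---|
| Before the end-of-visit questionnaires | 0 | 2 of 2 |
| After them, before the next-day contact | 1 | 1 of 2 |

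**3. Time since dosing at withdrawal (G.2).** During the monitoring period: under 2 h. Between the start and end of the scan: 2 h to about 2 + 1.5 = 3.5 h, ignoring transfer time. Both are well inside the 12 hours for which Section I.3 asks participants to avoid driving. The protocol therefore itself expects relevant drug exposure after such a person has left.

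**4. What still applies.** Monitoring already completed stands, so someone who withdraws during the scan has had the full two hours. The on-call number is promised to all participants. The duty to report adverse events covers events that the team learns of. A doctor is called if the participant voices a concern. None of these is a scheduled question put to the participant after withdrawal.

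**5. How many people?** The protocol gives no rate of withdrawal after dosing. The 4 extra recruits in Section J.3 allow for data-quality problems and drop-out together, and do not say when drop-out happens. They cannot be turned into a rate, so no percentage is given here.

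**The case against.** The strongest reply is that nothing is misstated. The sentence says that procedures are not required, which protects the right to withdraw and leaves staff free to offer follow-up. That stands. A reader might infer that the protocol forbids observation after withdrawal or leaves dosed participants without cover, and the text supports neither. What remains of the point is that follow-up is left to individual discretion, with no instruction to offer it.

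The group is also narrow. People who refuse contact or cannot be reached would not be helped by any wording. Eligibility is reviewed just before the capsule (G.2), and urine testing is placed at the screening or study visit (G.3), so some of the Investigator's reasons should surface before dosing. This stands too. It leaves ineligibility or deviation found late, and people who choose to stop but would accept a call.

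A reader might further infer that everyone who ends the scan early loses both questionnaires. The documents do not support that. Section I.4, item 6 allows the scan session to be ended at any stage and does not call this withdrawal from the study. Such a person can go on to the end-of-visit questionnaires and the next-day contact.

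Some contact with a withdrawn participant is likely in practice, because non-completers are paid pro rata (G.7) and the next-day follow-up also handles reimbursement. But the protocol neither promises that contact to withdrawn participants nor requires a side-effect question in it.

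Finally, the questionnaire's items are not in the document, so the argument about sleep is conditional on their content.

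**Conclusion.** The point holds as a minor one. A stated rule, not merely a missing detail, ends the requirement for active side-effect collection in people already exposed: 2 of 2 scheduled questionnaires or 1 of 2, depending on when they leave. What is left is passive cover.

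The conclusion rests on reading G.5 as covering all withdrawals, which its wording does, and on there being some dosed participants who stop but would accept contact. Their number is unknown and probably small. Nothing here shows that harm would be missed in any given share of participants. The comparison of treatment groups is not affected either, since G.5 already excludes withdrawn participants from analysis. It is a cheap improvement to participant safety that could be made; the study does not depend on it.

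**What to change.** Replace the sentence in G.5 with wording such as:

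> *After withdrawal, no further research procedures will be required. A participant who has taken the study capsule will still be offered the Side Effects Questionnaire before leaving and the next-day side-effects questionnaire, unless they decline. These answers will be kept for safety reporting even though the participant's outcome data are excluded from analysis.*

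The last sentence is needed because the adjacent rule on excluding data would otherwise leave it unclear whether the answers are used or discarded.

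The cost is up to two assessments per dosed withdrawal, both already in the protocol and both open to refusal, so the right to withdraw is kept. Section G.2 puts the full next-day follow-up at 30 to 45 minutes, including debriefing and reimbursement. The questionnaire alone should take less, though its own length is not given. As a change to an approved protocol, it would go to the ethics committee with the next amendment.
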